TITLE: **3D ROTATIONAL CT ANGIOGRAM WITH EMBOLIZATION
GUIDANCE AND CBCT IN PROSTATE ARTERY
EMBOLIZATION**

Sponsor: **[name]**

**University of Miami
Interventional Radiology
[name]
[name]
[name]**

National Clinical Trial Identifier: **NCT03164629**

VERSION: **B**

Date of Protocol: **February 20, 2018**

1) **Protocol Title**

3D Rotational CT angiogram with Embolization guidance and CBCT in Prostatic Artery Embolization

2) **Primary Objective**

To ascertain the feasibility of cone-beam CT with Embolization Guidance software (Emboguide) to identify prostatic arteries and assist endovascular navigation, by projecting a 3D road map of prostatic arteries on live fluoroscopy, in order to differentiate them from non-target vessels. **The primary outcome measurement will be the time for prostatic artery catheterization.**

- For the cases using Emboguide this will be measured as the time from which the Emboguide is displayed on the live fluoroscopy to the time of prostatic artery catheterization. Emboguide display is in addition to the angiogram roadmap display.
- For the control cases this will be measured as the time from which the angiogram is displayed on the live fluoroscopy to the time of prostatic artery catheterization.

3) **Background**

Direct clinical translation – University of Miami has been performing Prostatic Artery Embolization (PAE) since 2014 and has significant experience with the procedure. Technical challenges are encountered on a routine basis. The combination of 3D rotational CT, Emboguide and cone beam CT has tremendous potential to standardize and optimize a software protocol to aid in identification, catheterization, and embolization during the technically challenging PAE procedure. The data from this feasibility study might be used for a subsequent grant proposal (individually or in conjunction with other proposals) to improve the safety and efficacy of PAE.

The proposed study is a proof of concept investigation to assess a new clinical application. Current technical challenges to the widespread adoption of PAE include identification and catheterization of arteries appropriate for embolization. Prostate arteries are frequently tortuous, with duplication or replacement and varying sites of origin, and due to the nature of the patient population, atherosclerosis further complicates identification and navigation. An imaging system that could assist with identification and catheterization has the potential to improve patient outcomes by facilitating more complete embolization, avoidance of non-target vessel occlusions, and reduction of radiation exposure time.

With the current proposal, the software application can be standardized and tailored to optimize safety and efficacy of prostate embolization, which has been shown in clinical trials to be an effective alternative treatment of enlarged prostate or bladder outlet obstruction.

Another advantage of the protocol is it may obviate the need for pre-procedure CT angiogram, further reducing radiation exposure and procedure time.

4) **Inclusion and Exclusion Criteria***

Inclusion criteria:

- 1) Patient is age 50 to 79, inclusive
- 2) Patients undergoing Prostate artery embolization for BPH or urinary retention
- 3) Patient has signed informed consent (able to consent).

Exclusion criteria:

- 1) Patients with biopsy proven prostate cancer
- 2) Patient weight of >300 lbs.

5) **Local Number of Subjects***

Approximately 50 patients will be enrolled at this investigator site no screening failures are anticipated since all 50 patients will receive PAE and cone-beam CT. Currently cone-beam CT is performed routinely for all PAE cases. 25 sequential patients will undergo PAE with 3D angiogram and Emboguide. This will be followed by 25 sequential patients who will undergo PAE with no 3D angiogram nor Emboguide.

6) **Study Timelines***

The study duration will be approximately one year from the start date. The enrollment will take about 8 months and data analysis will take about 3 months.

7) **Study Design/Procedures Involved**

This is a single center prospective study. The patients eligible for the PAE for benign prostate hyperplasia will be offered the study and informed consent will be obtained. Once patient has been referred to Interventional Radiology (IR) and prior to the clinic visit with the IR physician, the records of the patient will be accessed for screening purposes. Patients will be recruited for participation in the study during routine consultation for the prostate embolization procedure. The main challenge of the PAE procedure remains the identification of the prostatic arteries and their super-selective catheterization. Contrast enhanced cone-beam CT (Dyna-CT) is already performed at our center as part of the PAE clinical protocol to reduce the risk of non-target embolization, especially to the rectal, bladder and penile vasculature. We will initially obtain a 3D rotational selective angiography of the internal iliac artery for study group. This dataset will be called the PLANNING dataset. We will assess if superimposing the pre-catheterization 3D dataset (in which the physician marks the prostate and its arterial feeders), can be used as an Emboguide tool along with overlay from a conventional DSA. This will be transmitted to live fluoroscopy and be used as an aid to catheterization of the prostatic arteries in the study group.

Study Group

The following parameters will be recorded for the study group:

- Time for catheterization as defined above
- Time for planning dataset for each side
- Total dose area product
- Dose for planning dataset for each side
- Dose area product only for fluoroscopy
- Total procedural time: **from access to closure**
- Amount of contrast medium used

Control Group

The following parameters will be recorded for the control group:

- Time for catheterization as defined above
- Total dose area product
- Dose area product only for fluoroscopy
- Total procedural time: **from access to closure.**
- Amount of contrast medium used

The tortuosity of the vessels will be graded in each case and will be categorized into:

- 1- Mild
- 2- Moderate
- 3- Severe

This will be graded visually for every case and will be noted on the case report forms. We will also study the arterial supply to the prostate gland with any anatomic variants including duplicated prostatic arteries or prostate arteries arising from less common branches such as common gluteal-pudendal trunk, obturator artery, and inferior gluteal artery in all patients.

8) **Data Storage**

All data collected will be stored in a password protected database in a password protected computer of Interventional Radiology to which only the PI and study coordinator or other key research personnel have access.

Address: [name]
[name]
[name]

9) **Data Management***

The statistical analysis for the current study will be conducted as follows. The following variables and parameters will be collected:

- Time for catheterization

- Time for planning dataset for each side (This will be evaluated as the time from completion of the 3D angiogram to beginning of catheterization)
- Total dose area product,
- Dose for planning dataset for each side,
- Dose area product for fluoroscopy only,
- Total procedure time, and
- The amount of contrast media used.

Descriptive statistics (mean, median, range, and standard deviation) will be computed for the treatment group and the control group and values will be compared for the variables of interest.

Additionally, a statistical significance comparison between the study group (with guidance) and the control group (without guidance) will be computed for several parameters. Specifically, the differences in means and/or medians between the following variables and parameters will be analyzed using a T-test or a Mann-Whitney test (depending on normality of the distribution and other assumptions):

- Time for prostate artery catheterization for each group
- Total dose area product (this will include DAP from the planning dataset in the study group)
- Dose area product only for fluoroscopy,
- Total procedure time, and
- The amount of contrast medium used.

10) **Withdraw of Subject**

Patients can withdraw from the study at any time, without penalty or benefit. This study may be discontinued, without the patients consent, at any time by the study doctor, if he/she believes that participation in the study is no longer in their best interest.

11) **Risks to Subjects***

Subjects will have one or more medical imaging studies (x-ray like films) which use radiation (emission or transmission of energy in the form of waves or particles). The tests or treatments include a whole body CT scan. To give an idea about how much radiation **the patients** will get, we will make a comparison with an every-day situation. Everyone receives a small amount of radiation that cannot be avoided each year. Some of this radiation comes from space and some from naturally-occurring radioactive forms of water and minerals. This research gives your body the equivalent of about 3 extra years' worth of this natural radiation. Subjects will be exposed to radiation as per their standard of care treatment. The investigational group will be subject to additional radiation for the 3D

planning dataset, however this in turn might reduce the duration of prostate artery catheterization leading to similar or reduced radiation if the 3D dataset was not used.

12) **Potential Benefits to Subjects***

There are no current direct benefits for patients, however there may be advantages to future patients if it is determined that this technology can obviate the need for pre-procedure CT angiogram and increase the safety of the procedure by reducing the risk of non-target embolization.

13) **Sharing of Results with Subjects***

The results will not be shared with subjects as there is no direct advantage to the patient and they are not related to clinical outcomes of the procedure.

14) **Setting**

Patients will be identify and recruited at PAC Radiology Clinic. The study procedures will be performed at UMHC.

15) **Recruitment**

Patients who require PAE will be referred by their Urologist or will visit an Interventional radiologist. This is a single center study. The patients eligible for the PAE for BPH will be offered the study and informed consent will be obtained. Patients will be recruited for participation in the study during routine consultation for the prostate embolization procedure.

16) **Confidentiality**

Subject study files will be stored in a double locked cabinet to which only the investigators and research team have access. The address is [name]. The only member(s) of the study team with access to it will be [name]. The data will be stored for up to 2-3 years after the study is completed and will be destroyed in accordance with university policies thereafter.

17) **Provisions to Protect the Privacy Interests of Subjects**

The Investigators and research team will ensure that the subject understands that only their information from the procedure will be collected. No other follow up visits will occur. All study records will identify patients by study identification number.

18) **Compensation for Research-Related Injury**

Subjects will not be compensated.

19) **Economic Burden to Subjects**

Subjects will bear the cost that they will normally pay for their standard of care procedure but no additional costs associated with participation in the study.

20) **Consent Process**

Written Informed consent and HIPAA forms will be obtained to collect the data from those prospective subjects who agree to participate. Three copies will be obtained, the original will be kept in the subject's file with the research team, the second will be provided to the patient and last will be placed in the medical record so it can be scanned to UChart.

A partial waiver of HIPAA for screening purposes is being requested. Once patient has been referred to Interventional Radiology (IR) and prior to the clinic visit with the IR physician, the records of the patient will be accessed for screening purposes.

Non-English Speaking Subjects: The ICF will be translated into Spanish once we have received approval from the IRB.

21) **Process to Document Consent in Writing**

The research team will document the informed consent process for every participant who will prospectively participate in the study. Patients will be consented at PAC Clinic.

Address: Professional Art Center

[name]

[name]

22) **Drugs or Devices**

The device is the cone-beam CT 3D Embolization guidance software which is currently being used at UMHC for Interventional radiology clinical purpose only.

23) **Resources Available**

The Interventional Radiology Department has 14 IR attending physicians well trained in the fields of Interventional Radiology and Interventional Oncology. It also has a dedicated research team:

[name]: Clinical Research Coordinator has been in research since 2007

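### All 25 Emboguide patients precede all 25 controls, so the unadjusted test of catheterization time cannot separate an Emboguide effect from a change between periods

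*Combined protocol and SAP*

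**What the plan says.** Section 5 (Local Number of Subjects) allocates by order of entry. First, "25 sequential patients will undergo PAE with 3D angiogram and Emboguide"; then, "This will be followed by 25 sequential patients who will undergo PAE with no 3D angiogram nor Emboguide". No section describes randomisation, alternation, overlap in time or a reason for this order.

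Section 2 makes time to prostatic artery catheterization the primary outcome. Section 9 (Data Management) starts with descriptive statistics and goes on: "Additionally, a statistical significance comparison between the study group (with guidance) and the control group (without guidance) will be computed for several parameters". Differences in catheterization time and four other parameters "will be analyzed using a T-test or a Mann-Whitney test (depending on normality of the distribution and other assumptions"). No term for period, case order, operator or case mix is planned.

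Section 7 has tortuosity graded visually and anatomic variants studied in all patients, but Section 9 uses neither. Operator is not among the parameters listed in Section 7. Section 23 counts 14 attending physicians in the department without saying who performs the study cases.

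The stated purpose is modest. Section 2 opens "To ascertain the feasibility of cone-beam CT with Embolization Guidance software (Emboguide"), and Section 3 says "The proposed study is a proof of concept investigation to assess a new clinical application".

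**The concern.** The two groups never overlap in time. Anything that differs between the first and second half of enrolment, such as who operates, which patients are referred or general experience with the procedure, goes into the group difference with its full weight, and the planned test has no means of removing it.

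The error can go either way. If times fall over the study for every case, the later control block looks better and a real Emboguide benefit can be masked. If times happen to be longer in the control period, a benefit can appear where there is none. The documents do not show that drift exists or which way it would run. What is at stake is whether the p-value on the primary outcome says anything about Emboguide.

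**Working it through.** The plan states no alpha, power, effect size or SD, so there is no figure of its own to reproduce.

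**Inputs from the documents.** 25 Emboguide cases, then 25 controls (Section 5); an unadjusted two-sample test (Section 9).

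**Assumptions.** Two-sided 5% level; lognormal times with log-scale SD 0.5 or 0.7; t-test on log time; the drift, step and effect sizes below. Paired results are for SD 0.5 / 0.7. They come from the noncentral t distribution; simulation of the 50 ordered cases agrees within 0.3 percentage points.

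**1. Can any model separate group from period?** A design matrix with intercept, group and period has rank 2 of 3. No analysis can separate a step change between the blocks from the Emboguide effect.

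**2. Standard error of the group difference.** SE = SD × √(2/25) = 0.141 / 0.198.

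**3. Gradual fall in times, no true effect.** The mean case number is 13 in the first block and 38 in the second, a gap of 25. A fall of a fraction d per case shifts the log difference by −25 × ln(1 − d).

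| d | Fall over 50 cases, 1 − (1 − d)^50 | Shift | Shift / SE | Significant |
|---|---|---|---|---|
| 0.25% | 11.8% | 0.063 | 0.44 / 0.32 | 7.2% / 6.1% |
| 0.5% | 22.2% | 0.125 | 0.89 / 0.63 | 14.0% / 9.5% |

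At 0.5%, nearly all of these results show Emboguide slower (13.7% / 9.0%). Simulating the tests that Section 9 names gives similar error: Mann-Whitney 12.5% / 8.7%, raw-scale t-test 12.5% / 8.3%.

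**4. Power for a true 30% reduction.** The log effect is −ln(0.70) = 0.357, and the drift is subtracted from it.

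- No drift: 0.357 / SE = 2.52 / 1.80; power 69.5% / 42.3%.
- 0.25% per case: 0.357 − 0.063 = 0.294; power 53.1% / 30.7%.
- 0.5% per case: 0.357 − 0.125 = 0.231; power 36.1% / 20.9%.

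**5. Step rise in the control period, no true effect.** A 10% rise shifts the difference by ln(1.10) = 0.095, and a false benefit appears in 9.7% / 6.8% of trials, against 2.5% nominal. A 20% rise gives 24.3% / 14.5%.

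**6. Can adjustment rescue the comparison?** The correlation of group with case order is −0.866, so the variance inflation is 1 / (1 − 0.866²) = 4.0 and the SE doubles to 0.283 / 0.396. Power for the 30% reduction is then about 23% / 14% even without drift. The adjustment also assumes a straight line: under a 10% step with no effect it still returns a mean ratio of 1/1.10 = 0.909, the same as the unadjusted analysis.

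**7. Would concurrent allocation help?** Simulated permuted blocks of 2, 4 and 6, with drift from 0 to 0.5% per case, keep the error between 4.7% and 5.1% and power at about 69% / 42%.

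**8. What randomisation does not cure.** Suppose Emboguide cases start 0.24 log units slower and improve by 0.01 per Emboguide case. The average penalty is 0.24 − 0.01 × 12 = 0.12, and the test rejects in about 13% / 9% of trials in either order. This is a real slowdown during early use of the software, not confounding by period.

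**The case against.** The strongest reply is proportionality. This is a single-centre feasibility study of about 50 patients, description comes first, and no efficacy claim or power is stated. A sequential cohort is a common choice at this stage. The centre has performed the procedure "since 2014 and has significant experience with the procedure", and on timing, "The enrollment will take about 8 months and data analysis will take about 3 months". Both may limit drift. At 0.25% per case the error barely moves, and nothing in the documents supports the faster rate. With Emboguide first, general learning works against the software, so the order is conservative for that mechanism. The count of 14 physicians describes the department, not the study operators, and anatomic variants as well as tortuosity are recorded in everyone.

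Much of this stands as a limit on size. The drift is assumed, a change of operator is conjecture, and protection against false benefit from general learning is real. It does not answer the structural point. Section 9 plans a significance comparison on the primary outcome, and the feasibility label does not make a confounded p-value interpretable. An order that is conservative for one mechanism can still mask a benefit, and it gives no protection against longer times in the control period. Recording case mix helps with measured differences between patients but does not separate group from period.

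**Conclusion.** The concern holds and should be fixed. That group and period are fully confounded follows from Sections 5 and 9 alone and needs no assumption. The practical size is unknown. Under the assumed SDs and shifts, it ranges from negligible (about 6 to 7% error at 0.25% drift per case) to serious (10 to 14% error and about half the power lost at 0.5%), with false benefit possible if times rise in the control period. The direction of any bias cannot be determined from the documents. The feasibility aim limits the consequence: the descriptive results for each group remain usable, but the between-group p-value cannot be attributed to Emboguide.

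**What to change.** **If enrolment has not started.** In Section 5, replace the two blocks with 1:1 randomisation of the same 50 patients in small permuted blocks of varying size (for example 2, 4 and 6), with allocation opened after consent. Choose the block sequence to end exactly at 50: if random blocks are simply cut there, about one list in five gives 24 or 26 Emboguide patients. Record operator and case order, and plot Emboguide times by Emboguide case number to show software learning. The cost is a protocol and consent amendment, an allocation list, and operators switching mode between cases. No extra patients are needed, and the number receiving the planning dataset stays at 25.

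**If enrolment is under way or the blocks must stay.** State in Section 9 that the between-group comparison is exploratory. Report estimates with confidence intervals, plot times by case order, and add a trend-adjusted sensitivity analysis, noting that it does not correct a step change. A tortuosity-adjusted analysis is supportive only: the grade is visual, no blinding is stated, and only the study group has the 3D angiogram. These are text changes.

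**Randomising the remaining patients mid-trial** is an option only with its costs stated: a smaller concurrent comparison, and more patients given the additional planning-dataset radiation described in Section 11.

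- After 20 Emboguide patients: 15 v 15; power for a 30% reduction about 47% / 27% (SD 0.5 / 0.7); 20 + 30/2 = 35 Emboguide patients, 10 more than planned.
- After 25: 12 v 13; power about 40% / 23%; 25 + 25/2 = 37.5, so 37 or 38 Emboguide patients, 12 or 13 more than planned.

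### Vessel tortuosity and arterial variants are recorded in every patient, but the comparison of two sequential, non-randomised cohorts makes no use of them: no adjusted estimate is pre-specified

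*Combined protocol and SAP*

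**What the plan says.** - **Allocation (Section 5).** The first 25 patients in sequence receive the 3D angiogram and Emboguide. Then: "This will be followed by 25 sequential patients who will undergo PAE with no 3D angiogram nor Emboguide". No randomisation, matching or stratification is described.
- **Why anatomy matters (Section 3).** In describing the obstacles to finding and catheterizing the right arteries, the protocol says: "Prostate arteries are frequently tortuous, with duplication or replacement and varying sites of origin".
- **What is recorded (Section 7).** "The tortuosity of the vessels will be graded in each case and will be categorized into" three grades, and: "This will be graded visually for every case and will be noted on the case report forms". The arterial supply is also studied in all patients, with "any anatomic variants including duplicated prostatic arteries" and less common origins.
- **Which images exist.** Section 5 says that "all 50 patients will receive PAE and cone-beam CT". The 3D planning images belong to one group only (Section 7): "We will initially obtain a 3D rotational selective angiography of the internal iliac artery for study group". Section 2 indicates an angiogram roadmap in both groups. The image used for the visual grade is not named.
- **What is analysed (Section 9).** Catheterization time and four other parameters "will be analyzed using a T-test or a Mann-Whitney test (depending on normality of the distribution and other assumptions"). Tortuosity and variants appear neither in the Section 9 variable list nor in its tests. The document contains no regression, stratified analysis or table of anatomy by group.

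**The concern.** Cohort membership is fixed by order of enrolment, so comparability rests on the two runs of patients being alike. The protocol collects the anatomical features that it links to difficult catheterization, then gives them no role in judging or improving the comparison.

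Two things are at stake. First, if one cohort has harder anatomy, an unadjusted test cannot tell that difference from an effect of guidance. Second, even in balanced cohorts, leaving out a strong predictor of time costs power with only 25 per group. If the covariates are chosen after the results are known, an adjusted estimate loses much of its credibility, so the time to specify it is now.

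The value of adjustment depends on how the grade is made. A noisy visual grade removes only part of any confounding. A grade read from different images in the two groups, or given after a slow catheterization, can itself bias the adjusted result.

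**Working it through.** **The plan's own figure.** The 25 per group cannot be reproduced, because no significance level, power, effect size or SD is stated. Everything below except 25 v 25 and the three grades is an assumption, chosen to show scale.

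**1. Precision with comparable cohorts** (two-sided 0.05, 80% power, noncentral t). The noncentrality is d × √(25/2) / √v.
- Unadjusted: v = 1, 48 df. Detectable d = 0.809 SD; power for 0.6 SD is 54.7%.
- Adjusted: grade uses 2 df and variant 1, leaving 48 − 3 = 45 df. v = (1 − R²) × 47/44, where R² is the share of variance in log time that the graded anatomy explains and 47/44 allows for chance covariate imbalance.

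| R² | Detectable effect (SD) |
|---|---|
| 0 | 0.837 |
| 10% | 0.794 |
| 20% | 0.749 |
| 30% | 0.700 |

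Break-even is near R² = 1 − (0.809/0.837)² = 0.066.

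**2. Effect of grading accuracy.** Take 30% severe, true R² = 0.30, and sensitivity = specificity = a. The proportion graded severe is q = 0.3a + 0.7(1 − a). Usable R² = 0.30 × 0.21 × (2a − 1)² / [q(1 − q)].

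| a | q | Usable R² | Detectable effect (SD) | Power at 0.6 SD |
|---|---|---|---|---|
| 1.00 | 0.30 | 0.300 | 0.700 | 67.0% |
| 0.90 | 0.34 | 0.180 | 0.758 | 60.2% |
| 0.80 | 0.38 | 0.096 | 0.796 | 56.1% |
| 0.70 | 0.42 | 0.041 | 0.819 | 53.6% |

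At a = 0.75, q = 0.40 and usable R² = 0.30 × 0.21 × 0.25/0.24 = 0.066. In this scenario, then, adjustment stops paying in precision at about 75% accuracy.

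**3. Confounding, only if the cohorts differ.** Assume that severe anatomy doubles time, R² = 0.30, and guidance has no effect. With 20% severe in the study group and 40% in controls, the unadjusted ratio is exp(−0.20 × ln 2) = 0.87. Simulation of 20,000 trials, with a three-level grade and a non-prognostic variant in the model, gives:

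| Analysis | Ratio | False positives |
|---|---|---|
| Unadjusted | 0.87 | 13.0% |
| Adjusted, accuracy 100% | 1.00 | 4.8% |
| Adjusted, 90% | 0.95 | 6.4% |
| Adjusted, 80% | 0.91 | 8.9% |
| Adjusted, 70% | 0.89 | 10.7% |

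With 25% v 35% severe, false positives are 6.9% unadjusted and 4.9%, 5.1% or 5.7% adjusted at 100%, 90% or 80% accuracy. With balanced cohorts they are 4.9% unadjusted and 4.8% adjusted.

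**4. What adjustment can spoil** (balanced cohorts).
- Unequal reading, no true effect: if every severe case is found in the study group but only 80% or 60% in controls, the adjusted ratio is 0.96 or 0.92, with 6.1% or 7.8% false positives.
- Grade follows time: the SD of log time is √(0.21 × (ln 2)² / 0.30) = 0.58, so a true effect of 0.6 SD is a ratio of exp(−0.6 × 0.58) = 0.71. If 20% or 40% of grades simply follow the observed time, the adjusted ratio becomes 0.73 or 0.75, while the unadjusted ratio stays at 0.71.

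**The case against.** The strongest reply is that the harm is hypothetical. Both cohorts come from one centre under the same eligibility criteria, with about 8 months of enrolment, and no reason is given why anatomy should shift between them. Chance imbalance is common: with identical populations, severe cases differ by 5 or more of 25 in 11%, 17.5% or 20% of trials at a prevalence of 20%, 33% or 50%. But the unadjusted test already allows for it, and its average false-positive rate stays at 5%. This stands. A reader might infer that anatomy is a known confounder here; the documents do not support that.

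It is also fair that the study calls itself a feasibility and proof-of-concept investigation, and that adjustment leaves the larger threats alone. Calendar period and operator learning run with group by design, and Section 2 starts the clock from a different display in each group. This limits the priority, but the plan still tests the primary outcome for significance, and the covariates are already being collected.

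The scoring objection stands in part. In the study group the physician marks the arterial feeders on the 3D dataset before catheterization, so naming a common image does not erase that knowledge.

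A reader might also infer that left and right sides would be analysed as independent observations, with inflated error. The documents do not support that. Section 7 grades by case, the per-side wording is attached only to the planning items, and no side-level test is planned.

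**Conclusion.** The point holds as an omission. Measured potential confounders and probable predictors of the primary outcome have no place in the analysis of two sequential, non-randomised cohorts. This should be changed, though the omission does not invalidate the study.

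Its size depends entirely on assumed inputs. It ranges from no inflation of the false-positive rate (balanced cohorts) to about 13% (20% v 40% severe, with severe anatomy doubling time). Adjustment brings the 13% to about 5% with perfect grading, but only to about 11% at 70% accuracy. For precision, the detectable effect moves from 0.81 SD to between 0.84 SD (anatomy explains nothing) and 0.70 SD (30% of the variance).

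It would be tempting to conclude that an adjusted model makes the sequential comparison sound. It does not: the adjusted ratio is supportive evidence on one source of non-comparability.

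**What to change.** **Section 9.** Keep the unadjusted test. Add a pre-specified, supportive linear model of log(catheterization time) on group, tortuosity grade (three categories) and any arterial variant (yes/no), with one value of each per case. Report the adjusted ratio with its 95% CI beside the unadjusted result, and a table of both covariates by group.

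**Section 7.** Name the conventional angiogram as the scoring image in both groups, not the 3D planning dataset. Have existing staff record grade and variant before the catheterization clock starts, so that the score cannot follow the observed time.

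**State the limits.** Some unequal reading may remain, because the study-group physician has already marked the 3D dataset. Noisy grading gives only partial control. Period effects, operator learning and the different clock starts are untouched.

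**Cost.** Wording in two sections and three model degrees of freedom; no new data, images or staff. The downsides are slightly worse precision if the graded anatomy explains less than about 6.6% of the variance, and shrinkage of a true effect if grades are nevertheless influenced by observed time.
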